6.2 Determination of Protocol Deviations

On an ongoing basis and prior to unblinding, a combined PD report, including programmable and observable PDs will be reviewed by the Clinical Research Organization (CRO). Programmable PDs are those PDs that can be programmed from the data recorded in the clinical database. Observable PDs are PDs identified by CRAs or other team members. PDs will be classified as ‘Major’ or ‘Minor’ by the Biostatistics Lead (BL). In addition, Clinical Operations Lead (COL) will review PDs to identify trends that might be evident across sites or countries.

After primary review performed by the CRO Biostatistician and COLs, the PD combined report will be provided to the Sponsor for the oversight review and final agreement.

6.3 Exclusions of Individual Values for Safety Analysis

Some local and systemic adverse events (AEs) will be directly measured by the subject and will not be subject to a reconciliation process, even if they are biologically implausible. Therefore, these implausible measurements will be removed from the analysis but included in listings. Implausible measurements are summarized in the Table 6.3-1 below:

Table 6.3-1: Implausible Solicited Adverse Events

Parameter	Implausible measurements
Body temperature	$\leq 33^{\circ}\text{C}$ or $\geq 42^{\circ}\text{C}$
Erythema	Measurements ≥ 900 mm Measurements < 0 mm
Induration	Measurements ≥ 500 mm Measurements < 0 mm
Ecchymosis	Measurements ≥ 500 mm Measurements < 0 mm

7. ANALYSIS SETS

7.1 All Enrolled Set

All screened subjects who provide informed consent and provide demographic and/or other baseline screening measurements, regardless of the subject's randomization and vaccination status in the study, and received a subject ID.

7.2 Exposed Set

All subjects in the All Enrolled Set who receive a study vaccination.

7.3 Full Analysis Set (FAS), Efficacy/Immunogenicity Set

FAS, Efficacy: All subjects in the All Enrolled Set who received at least one dose of study vaccine and are evaluated for efficacy from 14 days after the last vaccination.

FAS, Immunogenicity: All subjects in the All Enrolled Set who received at least one dose of study vaccine and provide evaluable serum samples at both baseline and after the last vaccination.

Last vaccination is at Visit 2 for "previously vaccinated" subjects and at Visit 3 for "not previously vaccinated" subjects.

FAS will also be defined by time point and objective:

- *FAS-Eff1* will include all subjects ≥ 2 years to < 18 years of age who received at least one dose of study vaccine and are evaluated for efficacy from 14 days after the last vaccination (primary objective).
- *FAS-Eff2* will include all subjects ≥ 3 years to < 18 years of age who received at least one dose of study vaccine and are evaluated for efficacy from 14 days after the last vaccination (Co-primary objective).
- *FAS-HII* will include all subjects ≥ 2 years to < 9 years of age who received at least one dose of study vaccine and provide evaluable serum samples for HI analysis at both baseline and after the last vaccination (secondary objective).
- *FAS-MNI* will include all subjects ≥ 2 years to < 9 years of age who received at least one dose of study vaccine and provide evaluable serum samples for MN analysis at both baseline and after the last vaccination (exploratory objective).

In case of vaccination error, subjects in the FAS will be analyzed “as randomized” (i.e. according to the vaccine a subject was designated to receive, which may be different from the vaccine the subject actually received).

If a subject is unblinded during the study, he/she will be included in the FAS.

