For each “previously vaccinated” subject, two visits (Day 1, Day 22), one reminder telephone call after vaccination to remind the parents/legal guardians to complete the diary card (Day 3) and two safety follow up telephone calls (Day 91 and Day 181, or the end of influenza season, whichever is longer) are planned. Influenza surveillance will be performed weekly and during planned visits, during influenza season.

For each “not previously vaccinated” subject, three visits (Day 1, Day 29, Day 50), two reminder telephone calls after each vaccination to remind the subject and/or the parents/legal guardians to complete the diary card (Days 3, Day 31), and two safety follow up telephone calls (Day 120 and Day 209, or the end of influenza season,

whichever is longer) are planned. Influenza surveillance will be performed weekly and during planned visits, during influenza season.

In addition, all subjects may have additional unscheduled visits if they meet pre-defined study criteria for the unscheduled visit.

A subset of the subjects will have blood drawn, before each vaccination and at 3 weeks after last vaccination (resulting in 2 blood draws per subject in “previously vaccinated” subjects, and 3 blood draws per subject in “not previously vaccinated” subjects). Blood drawn in these subsets will be evaluated for antibody responses as measured by immunogenicity.

Weekly active influenza contacts for ILI will be conducted (when visit not scheduled) from Day 1 until the end of influenza season, or at early discontinuation).

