5.2 Vaccination Clinic Visits

Please refer to [Time and Events Table 3](#) and [5](#). Vaccination will be performed on Day 1 (all subjects) and Day 29 (“not previously vaccinated” subjects) using the vaccine identified by the assigned Pack ID.

The Day 1 (all subjects) and Day 29 (“not previously vaccinated” subjects) serology sample collected from subjects participating in the immunogenicity subset must be taken **prior** to vaccination.

After completing the pre-vaccination procedures as described in [Section 5.1, Vaccination Clinic Visit – Day 1 Pre-vaccination Procedures](#), the vaccine will be administered to the subject according to the procedures described in [Section 6.3, Vaccine Preparation and Administration](#), observing the blinding procedures described in [Section 3.3, Blinding Procedures](#).

Prior to administration of the study vaccination, it needs to be confirmed that the subject is eligible for vaccination and does not meet any criteria for exclusion or delaying study vaccination as described in [Section 4, Selection of Study Population](#).

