2.1.2 Primary and Co-Primary Endpoint

The primary and co-primary efficacy endpoint is the time from the last study vaccination to the onset of the first occurrence confirmed influenza by either RT-PCR-confirmed or culture-confirmed, due to any influenza Type A or B strain regardless of antigenic match to the strains selected for the seasonal vaccine, occurring > 14 days after the last vaccination and until the end of the influenza season.

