After randomization, all subjects will receive a dose of 0.5 mL of study vaccine to which they were assigned (QIVc or non-influenza comparator vaccine) on Day 1, administered intramuscularly in the deltoid muscle, preferably of the non-dominant arm. For those subjects who are “not previously vaccinated” a second administration will follow on Day 29, as presented below:

Table 3-2: Vaccination Schedule

Subjects	QIVc Group	Comparator Group
“previously vaccinated” ≥ 2 years to < 9 years of age, and ≥ 9 years to < 18 years of age	Day 1: QIVc	Day 1: Men ACWY
“not previously vaccinated” ≥ 2 years to < 9 years of age	Day 1: QIVc Day 29: QIVc	Day 1: Men ACWY Day 29: Saline

To maintain the observer-blind design of the study, the roles and responsibilities of “blinded” and “unblinded” team members will be defined. After vaccination, safety assessments and study related procedures and monitoring thereof must be performed by “blinded” team members.

This study is planned for at least three influenza seasons. Laboratory confirmed influenza cases will be reviewed on a regular basis (blinded review). If decided by the Sponsor, and after observing at least 50% of planned events meeting the co-primary endpoint, interim analyses for efficacy may be performed for evaluation by a DMC.

Study Definition of Influenza-Like-Illness and Influenza Case

An Influenza Like Illness (ILI) Case is defined as follows: The Centers for Disease Control and Prevention (CDC) criteria ILI is modified for young children for the purposes of this study to include additional symptoms): fever of $\geq 100.0^{\circ}\text{F}$ / $\geq 37.8^{\circ}\text{C}$ along with any of the following: cough, sore throat, nasal congestion, or rhinorrhea.

The ILI onset day is defined as the first day that the subject meets the primary protocol defined ILI.

The ILI end date is defined as the date the last symptom resolves.

A new ILI episode will only be taken into account after resolution of the previous one, as judged by the investigator (suggested interval between two ILI episodes is 14 symptom free days).

A detailed schedule and listing of procedures are shown in the Time and Events Tables 3-7 (see [protocol synopsis](#)).

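### SAP 7.3 places the last vaccination one visit (21 days) too late in the section that defines the efficacy and immunogenicity analysis sets

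*SAP*

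**What the plan says.** SAP 7.3 defines the full analysis sets for efficacy and immunogenicity together. Membership of the efficacy set requires at least one dose and that subjects "are evaluated for efficacy from 14 days after the last vaccination". The immunogenicity set requires that subjects "provide evaluable serum samples at both baseline and after the last vaccination".

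A separate paragraph follows, not limited to either set: "Last vaccination is at Visit 2 for" previously vaccinated subjects, and at Visit 3 for the others. FAS-Eff1 and FAS-Eff2, the sets for the primary and co-primary objectives, are defined after it with the same 14-day condition. SAP 7.4 repeats that condition for PPS-Eff1 and PPS-Eff2.

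The schedule elsewhere is different:

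- Protocol 5.2: "Vaccination will be performed on Day 1 (all subjects) and Day 29", the latter for subjects not previously vaccinated.
- SAP section 3, introducing Table 3-2: for these subjects "a second administration will follow on Day 29".
- Protocol 3.1: previously vaccinated subjects have "two visits (Day 1, Day 22") and subjects not previously vaccinated have "three visits (Day 1, Day 29, Day 50").

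The primary endpoint in SAP 2.1.2 "is the time from the last study vaccination to the onset of the first occurrence" of confirmed influenza. It names no visit.

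**The concern.** The SAP's only statement tying the last vaccination to a visit names visits at which nobody is vaccinated. It stands in the section that determines who enters the primary analysis. A programmer who builds the set flags from 7.3 alone would start the 14-day condition from the Day 22 or Day 50 visit.

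Two things are at stake. First, subjects who leave in the gap between the true and the stated start would be excluded from the primary population after randomisation, for a reason nobody intended. Second, the immunogenicity set would require a sample that the schedule does not provide.

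There is also a smaller mismatch. Section 7.3 says from 14 days, while SAP 2.1.2 and 11.1 say more than 14 days.

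**Working it through.** **1. Visit numbers and days (protocol Tables 3 and 5)**

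| Group | Visit 1 | Visit 2 | Visit 3 | Vaccine given at | SAP 7.3 says last dose at |
|---|---|---|---|---|---|
| Previously vaccinated | Day 1 | Day 22 | safety call, Day 91 (Table 4) | Visit 1 | Visit 2 |
| Not previously vaccinated | Day 1 | Day 29 | Day 50 | Visits 1 and 2 | Visit 3 |

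The urine specimen text in protocol 3.5 agrees: pregnancy testing precedes vaccination at visit 1 and, for the two-dose group, at visit 2.

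**2. The plan's own interval.** SAP 2.2.4 places the immunogenicity assessment 21 days after the last dose. The schedule reproduces this: 22 − 1 = 21 and 50 − 29 = 21.

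**3. Size of the error.** Section 7.3 puts the last vaccination on the serology day, so it is late by the same 21 days in both groups. The Day 22 and Day 50 visits have a window of −1 to +4 days. With the doses on their nominal days:

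- Previously vaccinated: 21 − 1 = 20 to 26 − 1 = 25 days.
- Not previously vaccinated: 49 − 29 = 20 to 54 − 29 = 25 days.

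**4. Start of the 14-day condition**

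| Group | From the true last dose | From SAP 7.3 read literally |
|---|---|---|
| One dose | 1 + 14 = Day 15 | 22 + 14 = Day 36 |
| Two doses | 29 + 14 = Day 43 | 50 + 14 = Day 64 |

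**5. Who would be excluded.** These are subjects whose follow-up ends between the two columns. The protocol plans for about 10% dropout but does not say when it occurs. Assume it is spread evenly over the 180 days after the last vaccination:

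- 21 days: 10% × 21/180 = 1.2% of subjects, or 0.0117 × 7,692 ≈ 90.
- 20 to 25 days: 10% × 20/180 = 1.1% to 10% × 25/180 = 1.4%.
- If follow-up instead lasts 270 days (about the upper end of the 6 to 9 months in the synopsis): 10% × 21/270 = 0.8%.

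More dropout soon after vaccination would raise the share, and later dropout would lower it.

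**6. Immunogenicity set.** The last scheduled blood draw is Day 22 or Day 50 (protocol 3.5). If the last vaccination were at that visit, no scheduled sample would follow it.

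**7. From 14 days against more than 14 days.** For a Day 1 dose, from 14 days begins on Day 15 and more than 14 days begins on Day 16. For a Day 29 dose the days are 43 and 44. The difference is one day.

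**The case against.** The strongest reply is that the intent is plain. The sentence directly follows the immunogenicity definition. The matching protocol text (8.3.4) names Day 50 and Day 22 as the time points for data after the last vaccination, and SAP 2.2.4 gives the same days for serology. SAP Table 3-2 has no dose on Day 22 or Day 50, so a programmer would find no vaccination record there. On this view it is a misworded statement of the serology visit. That is very probably right about intent, but it does not repair the text. The sentence carries no limit to immunogenicity, precedes the efficacy subsets, and read literally fails for the immunogenicity set as well.

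A reader might go further and infer that the case window opens 21 days late and that endpoint cases are lost. The documents do not support that. Section 7.3 settles who is in the set, not which illnesses count. SAP 2.1.2 and 11.1 and protocol 3.1 and 8.1.1.2 all count from the last vaccination itself and use no visit number. Case counting would be delayed only if someone carried the 7.3 labels into the endpoint derivation, against those sections.

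A reader might also infer that children who become cases in the 21 days would drop out of the FAS. That does not follow either. Surveillance is weekly to the end of the season (protocol 5.3.3), and there is a safety call 30 days after illness onset (protocol 5.4.1). A case does not end observation. Only a child who also left the study before Day 36 or Day 64 would be affected.

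The one-day mismatch is minor. The endpoint and the analysis section agree on more than 14 days, so the operative rule is clear, and only 7.3 and 7.4 need to match it.

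**Conclusion.** The visit labels in SAP 7.3 are wrong by one visit in both groups. They contradict protocol Tables 3 and 5 and the SAP's own Table 3-2. That part is certain and rests on no assumption.

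The direct effect of a literal reading is on membership of FAS-Eff1, FAS-Eff2, PPS-Eff1 and PPS-Eff2. It amounts to roughly 1% of subjects, resting on the planned 10% dropout and an even spread over 180 days, which the documents do not state. The immunogenicity FAS would have no qualifying scheduled sample. The primary endpoint, its clock and the case window are unaffected as written. No bias in vaccine efficacy has been shown.

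The likely practical effect is small because the intent can be inferred from other sections. It is still an error in the definition of the primary population and should be corrected before unblinding.

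**What to change.** In SAP 7.3:

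1. Replace the sentence with one saying that the serum sample after the last vaccination is taken at Visit 2 (Day 22) for previously vaccinated subjects and at Visit 3 (Day 50) for subjects not previously vaccinated. Limit it to the immunogenicity sets.
2. Define the efficacy FAS, including FAS-Eff1 and FAS-Eff2, by the actual date of the last study vaccination received, with evaluation more than 14 days after that date. Using the actual date also covers a two-dose child who received only the first dose, whom no fixed visit label fits.
3. Make the same change to PPS-Eff1 and PPS-Eff2 in SAP 7.4.

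The endpoint text in SAP 2.1.2 needs no change. The cost is SAP wording only: no new data, no change to the schedule and no effect on the event targets.

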7.4 Per Protocol Set (PPS), Efficacy/Immunogenicity Set

All subjects in the FAS Efficacy/Immunogenicity who:

- Correctly receive the vaccine (i.e., receive the vaccine to which the subjects is randomized and at the scheduled time points).
- Have no major protocol deviations leading to exclusion (see [Section 6.1](#)) as defined prior to unblinding / analysis.
- Are not excluded due to other reasons (e.g. subjects who withdrew informed consent) defined prior to unblinding or analysis (see [Section 6.2](#))

PPS are subsets of FAS and should be always defined even if the objectives do not require it.

In case of vaccination error, subjects in the PPS will be analyzed “as randomized” and the subject who received the wrong vaccination will be excluded from the PPS. If a subject receives a vaccine from the wrong kit number, but the same as the one the subject was randomized to, the subject will not be removed from the PPS.

Subjects randomized in the wrong stratum will be excluded from the PPS.

If a subject is unblinded during the study, except for SUSAR, he/she will be excluded from the PPS.

Similarly to FAS, PPS will also be defined per objective and time point.

- *PPS-Eff1* will include all subjects ≥ 2 years to < 18 years of age who received at least one dose of study vaccine and are evaluated for efficacy from 14 days after the last vaccination (primary objective).
- *PPS-Eff2* will include all subjects ≥ 3 years to < 18 years of age who received at least one dose of study vaccine and are evaluated for efficacy from 14 days after the last vaccination (Co-primary objective).

- *PPS-HII* will include all subjects ≥ 2 years to < 9 years of age who received at least one dose of study vaccine and provide evaluable serum samples for HI analysis at both baseline and after the last vaccination (secondary objective).
- *PPS-MNI* will include all subjects ≥ 2 years to < 9 years of age who received at least one dose of study vaccine and provide evaluable serum samples for MN analysis at both baseline and after the last vaccination (exploratory objective).

Exclusions will be considered by objective/time point, i.e., sometimes not all data of a subject but only part of the subject's data will be removed from the PPS analysis.

7.5 Safety Set

Solicited Safety Set (solicited local and systemic adverse events and other solicited adverse events)

All subjects in the Exposed Set who have gone through any assessment of local and systemic site reaction and/or assessment of any use of analgesics/antipyretics.

Unsolicited Safety Set (unsolicited adverse events)

All subjects in the Exposed Set who have gone through any adverse event assessments i.e., a subject does not have to have any adverse events to be included in this population.

Overall Safety Set

All subjects who are in the solicited safety set and/or in the unsolicited safety set.

Subjects providing only 30 minutes post-vaccination safety data will also be reported separately in a 30-minute post-vaccination safety analysis.

In case of vaccination error, subjects will be analyzed as “treated” (i.e., according to the vaccine a subject receives, rather than the vaccine to which the subject is randomized).

Subjects randomized in the wrong stratum will be reassigned to the correct stratum and will be analyzed using corrected stratum for all safety sets (i.e., solicited safety set, unsolicited safety set and overall safety set). If a subject is unblinded during the study, he/she will be included in all the safety sets.

7.5.1 Restricted Safety Set

Not applicable.

7.6 Other Analysis Set

Not applicable.

8. GENERAL ISSUES FOR STATISTICAL ANALYSES

8.1 Adjustment for Covariates

The estimate of the hazard ratio and the respective estimate for absolute vaccine efficacy (aVE) and pertaining two-sided 95% confidence intervals will be calculated based on the Cox proportional hazards model with vaccine group as the main effect. Randomization stratifying factors (i.e by age stratifying factors, season) as well as previous influenza vaccination will be modelled as random effects as suggested by [Kahan and Morris \(2012\)](#). In case of computational difficulties due to small number of events, an unadjusted hazard ratio will be estimated and reported (for example, in a subgroup analysis).

The log₁₀-transformed antibodies at Day 1, Day 22, and Day 50 for not previously vaccinated subjects and Day 1 and Day 22 for not previously vaccinated subjects will be modeled using an Analysis of Covariance (ANCOVA) model with a factor for vaccination group, age-group, baseline-titer, country and previous influenza vaccination. Summary tables will show both adjusted and unadjusted GMTs and adjusted and unadjusted ratios of GMTs for each vaccine group, except for subgroup analyzes which will present unadjusted estimates only.

Binary data tables will show unadjusted percentages.

The statistical models for efficacy might be reduced in case they fail to converge.

8.2 Handling of Dropouts, Missing Data

The analyses will be done without adjustments for missing values.

8.2.1 Safety Data

For unsolicited adverse events, the entire study period will be divided into the following intervals: Day 1 to Day 22, Day 23 to Day 181 in “previously vaccinated” subjects and Day 1 to Day 50, Day 51 to Day 209 in “not previously vaccinated” subjects.

For solicited adverse events, the solicited study period 30 min - Day 7 after each vaccination will be divided into: 30 min and Day 1-7 (without the 30-minute interval).

No imputation of missing solicited or unsolicited AEs will be used. The percentage of subjects with missing solicited AE assessments and missing safety phone calls or safety assessment, including subjects who discontinued the study, will be reported for each time.

8.2.2 Immunogenicity Data

Missing immunogenicity values are considered ‘missing completely at random’ (MCAR) and therefore will not contain information that impact the result of the analysis (i.e., not informative). Imputation methods will therefore not be used.

The secondary immunogenicity objectives will be analyzed using the FAS immunogenicity. The exploratory immunogenicity objectives will be analyzed in the similar manner as the secondary immunogenicity objectives.

If the percentage of vaccinated subject excluded from the FAS (immunogenicity) is greater than 5%, a secondary analysis based on the PPS will be performed to complement the FAS. The exploratory immunogenicity objectives will be analyzed on the FAS only.

8.2.3 Efficacy Data

Primary efficacy data will be analyzed using FAS as primary analysis set but the analysis will be repeated on PPS for robustness, irrespective of the difference in size between the two analysis sets.

The following algorithm will be applied:

1. If less than 20% of subjects are without efficacy data, then the analyses (e.g., ILI swabs collected without any RT-PCR assessment record) will be run on FAS and PPS and no further statistical evaluation will be performed.
2. If observations are missing for 20% or more of subjects, the missing mechanism will be analyzed by vaccine group using a newly created variable indicating whether a subject’s efficacy-value is missing or not (1=efficacy record present; 0=efficacy record not present). It will be tested, by chi-square test, if the proportion of missing observations/subjects varies significantly between vaccine groups. If the difference is significant with $P < 0.05$ then a sensitivity analysis will be performed of the primary efficacy analysis imputing randomly x% (from 0% to 100% in 10% increments) of missing data as PCR-confirmed cases.

